The primary objective of this study is to evaluate an active venting system across domains of sound quality and occlusion. More specifically, researchers hypothesize that a dynamic venting system will provide better streaming sound quality than coupling achieved with an open dome. Additionally, researchers hypothesize that a dynamic venting system will provide better quality of their own voice (less occlusion effect) than with coupling achieved with vented domes.

3 Description of the investigational device

The overall intended purpose of the device is to amplify and transmit sound ot the ear and thereby compensate for impaired hearing. The dynamic receiver features a mechanically

switching vent that is seamlessly steered by the automatic operating system of the hearing aid. It combines the hearing performance of the a closed fit with the comfort of an open fit.

4 Design of the clinical investigation

This confirmatory study will have 3 conditions across two tasks. One task will be investigating streaming sound quality and the other will investigate own voice perception (occlusion effect). The sample population will be of 15-20 human subjects. The order of conditions will be counterbalanced and the participants will be blinded to the conditions.

5 Risks and benefits of the investigational device and clinical investigation

There are minimal risks associated with both the investigational device and participating in the clinical investigation. Identified risks are no greater than those associated with the daily use and wear of approved, available hearing aids. The device used presents non-significant risk per FDA.

The benefits of participating in the investigation include the possibility of hearing sounds that have not been previously heard, such as speech and environmental sounds, which may improve communication in daily life. Subjects may experience the benefit of personal satisfaction for participating in research to improve hearing instrument technology. Subjects will also be compensated for their time in participating in this study.

There are no known or anticipated risks to subject hearing ability associated with participation in this study. All sounds used in this study will be presented at safe listening levels. While using hearing aids, the following are possible occurrences:

•Cerumen impaction

•Ear discomfort, pain or soreness

•Sweat or moisture accumulation in the ear canal or pinna

•A feeling of pressure or fullness in the ear

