•Itching, blisters, or sores in the ear canal or pinna

•Headache

•Redness of tissue

The research personnel will review these risks with the subjects and answer any questions they have. Hearing aids are not a significant risk investigational device as defined in the FDA 21 CFR 812.3(m).

6 Endpoints

Primary endpoint: Subjective ratings of the coupling conditions, for both streaming sound quality and own voice perception (occlusion effect). These will be administered via a 100 point scale, from 0 to 100 (0 = least preferred, 100 = most preferred). For streaming sound quality, participants will be presented with a pop song and will be asked to adjust the volume to their most comfortable level before making a rating. For the own voice perception portion, participants will be asked to read the Rainbow Passage prior to making a rating.

Secondary endpoint: Analysis of audio recordings of participants reading the Rainbow Pas-sage (for occlusion investigation). Given the Lombard effect, researchers believe there to be a possibility that subjects will adapt certain qualities of their voice depending on the level of occlusion. This secondary measure may give insight to such phenomenon and supplement further understanding of the primary objective.

7 Inclusion and Exclusion Criteria

Inclusion criteria:

18+ years of age

Hearing loss must be within the recommended fitting range and candidacy guidelines for the study devices and couplings.

Participants must indicate no prior history of problematic tinnitus or pain/discomfort from loud sounds.

Hearing loss must be symmetrical below 500 Hz (<= 10 dB) and sensorineural etiology Exclusion criteria:

Unable or unwilling to have two appointments lasting approximately 2 hours each

Unable or unwilling to wear devices for study appointments

Active middle or outer ear drainage, infection, redness, swelling within 90 days of appointments

8 Measurements and procedures

Participants will be seen for two appointments. The first appointment will consist of updating the audiogram and taking earmold impressions.

The second appointment will last approximately one hour.

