Two sets of comparisons will take place investigating streaming sound quality, and own voice tolerance. To compare streaming sound quality, participants will listen to a streamed music signal under the following conditions – dynamic vent receiver using a custom earmold in the closed position, SDS 4.0 receivers coupled with appropriately fitting open domes, as well as SDS 4.0 receivers coupled with vented domes. Conditions will be counterbalanced and randomized. Participants will listen to a 30 second excerpt of a pop song and make an absolute sound quality rating for each condition. To compare own voice tolerance, participants will read the rainbow passage (Fairbanks, 1960) under the following conditions - dynamic receiver in the open position compared to SDS 4.0 receivers coupled with appropriately fitting vented domes and open domes. Participants will be asked to give an absolute rating for both sets of comparisons-streaming sound quality, and quality of own voice.

All analysis of the results will occur at the conclusion of the study. Paper questionnaires will be digitized for statistical analysis. Audio recordings will be anonymized and saved as .wav files to be used for an intensity analysis. These will be stored on a company network drive.

9 Statistical design and analysis

A power analysis was conducted prior to the investigation. For a repeated measures ANOVA, a sample size of 20 participants is deemed adequate to detect a medium effect size (.3) with a power of 80%. This assumes a nonsphericity correction of 1. In the event that the dataset is not normally distributed, a rational arcsine unit transformation will be performed prior to per-forming the statistical analysis.

10 Investigation Duration

Expected participation for each subject is two days. The entire investigation is expected to last 2-4 weeks.

11 Data handling and management

Electronic or paper based CRFs will be used to capture the participant data. If electronic, subjective questionnaires will be available in the EDC system and the participant will be able to read question and choose answer. If paper based subjective questionnaires are used, the participant will answer each question and the results will be transferred to the EDC by the investigator. Objective data will either be entered in directly to the EDC system, or transferred from a paper based CRF into the EDC system.

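### Section 9 names and powers only a three-condition repeated measures ANOVA, whose overall test does not answer either directional pairwise hypothesis in Section 2

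*Combined protocol and SAP*

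**What the plan says.** - Section 2, streaming: "More specifically, researchers hypothesize that a dynamic venting system will provide better streaming sound quality than coupling achieved with an open dome".
- Section 2, own voice: "a dynamic venting system will provide better quality of their own voice (less occlusion effect) than with coupling achieved with vented domes".
- Section 4: "This confirmatory study will have 3 conditions across two tasks".
- Section 6 makes the 0 to 100 ratings on both tasks the primary endpoint. It names no pair of conditions and no criterion.
- Section 8 lists three conditions for each task. For own voice these are "dynamic receiver in the open position compared to SDS 4.0 receivers coupled with appropriately fitting vented domes and open domes". For streaming they are the dynamic receiver closed, open domes and vented domes.
- Section 9: "For a repeated measures ANOVA, a sample size of 20 participants is deemed adequate to detect a medium effect size (.3"), with 80% power. "This assumes a nonsphericity correction of 1". The only other analysis rule there is a conditional rational arcsine transformation.

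No section gives a contrast, a follow-up test, alpha, sidedness, a multiplicity rule or a success rule.

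**The concern.** Each hypothesis concerns two conditions and a direction. The overall F of a three-condition ANOVA asks whether any of three means differ. The third condition (vented dome for streaming, open dome for own voice) can make it significant alone, and so can a dynamic vent that is rated worse than its comparator. A pairwise test must therefore follow, and the text allows several procedures that differ in power and in error control. If the procedure is settled after the ratings are seen, neither hypothesis has a prespecified test, although both form the primary objective of a study described as confirmatory. The stated power also cannot be read as the power to confirm either hypothesis.

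**Working it through.** **Inputs from the documents.** N=20, effect .3, power 80%, nonsphericity correction 1 (Section 9); three conditions and two tasks (Section 4).

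**Assumptions, not in the documents.** The .3 is Cohen's f; alpha .05, two-sided; compound symmetry; correlation ρ=.5 between conditions, with .3 and .7 as a range.

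**1. The plan's own figure.** For one task, the noncentrality is λ = N·3·f²/(1−ρ) with df 2 and 38.
- ρ=.5: λ = 20·3·.09/.5 = 10.8, power 81.4%.
- ρ=.3: λ = 5.4/.7 = 7.71, power 66.4%.
- ρ=.7: λ = 5.4/.3 = 18.0, power 96.3%.

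The stated 80% is consistent with overall-F power for one task at a correlation near .5.

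**2. What a significant F shows.** λ depends only on the spread of the three means, not on which condition has which mean. At ρ=.5, F therefore rejects in the same 81.4% of trials when the hypothesised pair is equal and only the third condition differs, and when the dynamic vent is the worse of the pair. By simulation, a significant F together with a significant pair in the hypothesised direction then occurs in about 2.4% and 0% of trials.

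**3. Power for the hypothesised pair.** Holding f=.3, the standardised difference d depends on the pattern of means:
- Pair are the extremes of three evenly spaced means: d = .3·√6 = .735.
- One member of the pair differs from two equal conditions: d = .3/√(2/9) = .636.
- Pair is a half-step apart (neighbours among evenly spaced means): d = .735/2 = .367.

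The paired t has df 19, dz = d/√(2(1−ρ)) and noncentrality dz·√20. The last two columns are simulated.

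| Pattern | Paired power, ρ=.3 | ρ=.5 | ρ=.7 | F significant, pair not (ρ=.5) | F, then unadjusted pair (ρ=.5) |
|---|---|---|---|---|---|
| Extremes | 75.0% | 87.6% | 98.0% | 1.1% | 80.4% |
| One differs | 62.7% | 77.0% | 93.6% | 8.8% | 72.6% |
| Half-step | 26.1% | 34.5% | 52.1% | 48% | about 34% |
| Pair equal | 5% (alpha) | 5% | 5% | 76% | not a true effect |

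**4. Which patterns are likely.** Section 1 argues that a closed vent keeps low frequencies that open fittings lose when streaming, and that an open vent gives a more natural own voice. For streaming this suggests closed dynamic highest, open dome lowest and vented dome between (extremes). For own voice it suggests open dynamic and open dome similar, with the vented dome lower (one differs). The first two rows fit the rationale best.

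**5. Effect of the unstated choices (ρ=.5; extremes, one differs).**
- Direct paired test, one-sided .05: 93.6%, 86.4%.
- F, then Bonferroni over three pairs: 72.6%, 58.7%.
- If either hypothesis alone supports a claim, two unadjusted tests on independent tasks give 1−.95² = 9.75% chance of any false significance.
- Holm across two independent tasks with the same pattern in both: P(p≤.025) + P(.025<p≤.05)·P(other p≤.025). Extremes: .7951+.0811·.7951 = .860. One differs: .6609+.1094·.6609 = .733. Half-step: .2403+.1046·.2403 = .265.
- If both must succeed, independent tasks, same pattern: from .627² = 39% (one differs, ρ=.3) to .980² = 96% (extremes, ρ=.7). Half-step runs from .261² = 7% to .521² = 27%.

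**The case against.** The strongest reply is that the gap is narrower than it looks. Section 2 names the pair and the direction for each task. Section 9 mentions the ANOVA only in a power sentence and never refers to an overall F, and planned contrasts can be made within that model. Under the patterns that Section 1 suggests, F would rarely be significant without the pair (1.1% and 8.8%). The study is small and of non-significant risk.

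Much of this stands, and it rules out several stronger readings that a reader might infer:
- *The plan treats a significant F as proof of a hypothesis.* It does not say so.
- *The analyst may choose which pair answers each hypothesis.* Section 2 settles that. What is open is the procedure, alpha, sidedness and success rule.
- *The study is underpowered for its hypotheses.* Not shown: paired power can be above or below 80%, depending on unstated inputs.
- *The error rate is 9.75%.* That needs a rule that either hypothesis suffices, and the documents contain no such rule.

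What the reply does not supply is the test. A contrast that could be made within an ANOVA is not a contrast that has been specified, and the available routes differ by about 15 points of power for extremes (87.6% against 72.6%) and 18 for one differs (77.0% against 58.7%).

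**Conclusion.** The concern holds: the one analysis that is named and powered is not the one the two primary hypotheses need. The argument about direction and the third condition needs no assumption beyond the three-condition design. The percentages do rest on assumptions. The match to 80% depends on the effect metric, alpha and correlation, none of which is stated, so the documents support calling it consistent with overall-F power and no more. The 76% mismatch describes an equal pair, which is not the pattern that Section 1 leads one to expect. It shows what a significant F permits; it is not a forecast. Because both primary hypotheses are affected and the repair is small, the change should be made before the ratings are analysed.

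**What to change.** In Section 9:
- Make the primary analysis two prespecified paired contrasts: streaming, dynamic (closed) minus open dome; own voice, dynamic (open) minus vented dome.
- Report each with a 95% CI in rating points, and test each directly without requiring a significant F.
- State alpha, sidedness and whether one or both hypotheses must succeed. Adjust for multiplicity, for example by Holm, only if either alone suffices.
- Keep the three-condition ANOVA and the other pairs as supportive.
- Restate power for the two contrasts, giving the assumed correlation and pattern of means.

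**Cost.** One paragraph and no new data. If Holm is used, the loss against an unadjusted direct test at correlation .5, with the same pattern in both tasks, is 1.6 points for extremes, 3.7 for one differs and 8.0 for half-step. Holm is not always the more powerful route: for half-step it falls below F followed by an unadjusted pair, though that route does not control error across the two tasks. If both hypotheses must succeed, no split of alpha is needed, but joint power varies too widely with the correlation and the pattern of means for a single figure to be firm. The sponsor should state the assumptions behind whichever figure it adopts.

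### Section 9 names and powers only a repeated measures ANOVA, at epsilon = 1 and with no sphericity correction, although both confirmatory hypotheses are two-condition contrasts

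*Combined protocol and SAP*

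**What the plan says.** Section 9 (Statistical design and analysis) names one method, an ANOVA with repeated measures, and does so only in its power statement. There it says that "a sample size of 20 participants is deemed adequate to detect a medium effect size (.3) with a power of 80"%. The next sentence gives the sphericity input: "This assumes a nonsphericity correction of 1". The only data-dependent step is a rationalised arcsine transformation if the data are not normal. Section 9 gives no alpha, no correlation among the repeated ratings, no sphericity check or correction, and no follow-up contrast or error term.

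Section 4 says: "This confirmatory study will have 3 conditions across two tasks". It also says: "The sample population will be of 15-20 human subjects". Section 8 lists the streaming conditions as "dynamic vent receiver using a custom earmold in the closed position, SDS 4.0 receivers coupled with appropriately fitting open domes", plus SDS 4.0 receivers with vented domes. The own-voice task compares the dynamic receiver, now in the open position, with the same two dome couplings.

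Section 2 (Objectives) states two directional hypotheses. The dynamic vent is to beat the open dome on streaming sound quality, and the vented dome on quality of own voice.

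**The concern.** Two gaps meet here.

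First, the analysis that is named and powered does not match the hypotheses. A three-condition F test asks whether any of the means differ. It can reject because the two domes differ from each other, which is not a study hypothesis. The 80% is therefore the power of neither stated comparison.

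Second, the F test, and any contrast that borrows its pooled error, is valid at its nominal level only if the three pairwise differences have equal variance (epsilon = 1). The design gives reason to doubt this. In each task two conditions share a receiver and differ in dome, while the third uses another receiver; the couplings also differ in openness. If two conditions are rated more alike than either is to the third, the differences involving the third are more variable than the pooled error implies. In a study that calls itself confirmatory, the choice of error term should be fixed before the data are seen.

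**Working it through.** **1. Reproducing the plan's figure.** From Sections 4 and 9: n = 20, m = 3 conditions, effect size .3 (read as Cohen's f; the index is not named), epsilon = 1. Assumed, because not stated: alpha .05 and correlation ρ = .5.

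λ = f²·n·m·ε/(1−ρ), df1 = (m−1)ε, df2 = (n−1)(m−1)ε.

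At ε = 1: λ = .09 × 20 × 3/.5 = 10.8, with 2 and 38 df. Power is 81.4%. At n = 19 it is 79.1%, so 20 is the smallest sample reaching 80%, and the plan's figure reproduces under these assumptions.

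**2. Sensitivity by the same formula, n = 20.**

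| ε | λ | df | Power |
|---|---|---|---|
| 1 | 10.80 | 2; 38 | 81.4% |
| .95 | 10.26 | 1.9; 36.1 | 79.9% |
| .90 | 9.72 | 1.8; 34.2 | 78.2% |
| .75 | 8.10 | 1.5; 28.5 | 72.4% |

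**3. Type I error if sphericity fails.** The documents give no correlations, so three patterns are assumed, with equal variances of 1, dome-dome correlation r_d and dynamic-dome correlation r_y. The two independent contrasts then have variances a = 1 − 4r_y/3 + r_d/3 and b = 1 − r_d, and ε = (a+b)²/[2(a²+b²)]. For .7/.4: a = .7, b = .3, ε = 1/1.16 = .86. For .8/.4: a = .733, b = .2, ε = .75. For .9/.3: a = .9, b = .1, ε = 1/1.64 = .61.

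The pooled error stands for the average variance of the three differences. A dynamic-dome difference has variance 2 − 2r_y and the dome-dome difference 2 − 2r_d. The understatement is then:
- .7/.4: 1.2 against (1.2 + 1.2 + .6)/3 = 1.0, ratio 1.20
- .8/.4: 1.2 against (1.2 + 1.2 + .4)/3 = .93, ratio 1.29
- .9/.3: 1.4 against (1.4 + 1.4 + .2)/3 = 1.0, ratio 1.40

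Simulated type I error (normal data, n = 20, nominal 5%, 200,000 null datasets per pattern):

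| Pattern | ε | Uncorrected F | Greenhouse-Geisser F | Dynamic-vs-dome contrast, pooled error | Same contrast, own error |
|---|---|---|---|---|---|
| .7/.4 | .86 | 5.7% | 4.8% | 7.4% | about 5% |
| .8/.4 | .75 | 6.3% | 4.8% | 8.4% | about 5% |
| .9/.3 | .61 | 7.5% | 5.1% | 10.0% | about 5% |

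Over repeated runs the uncorrected F lay between 5.6% and 7.7%.

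**4. The omnibus power is not the contrast power.** Take exact sphericity, ρ = .5, f = .3, n = 20, so that a paired difference has SD √(2 × .5) = 1. If the dynamic vent differs equally from both domes, its difference from either is 3 × .3/√2 = .636 and the paired test has 77% power. If the untested dome lies midway between the tested pair, the difference is 2 × .3 × √1.5 = .735 and power is 88%. If the dynamic vent lies midway between the domes, the difference is .367 and power is 34%. The omnibus F has about 81% in all three cases.

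**5. Does lower epsilon always lower true power?** No. Greenhouse-Geisser power at n = 20, f = .3:

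| Pattern | ε | Dynamic differs from both domes | Open dome is the odd one out | Dynamic midway between the domes |
|---|---|---|---|---|
| .8/.4 | .75 | 72% to 73% | 84% | 88% |
| .8/.5 | .80 | 80% to 81% | 90% | 93% |

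**The case against.** The strongest reply is that Section 9 discloses its assumption and the stated power reproduces under it. Both points are correct, and three stronger readings that a reader might draw are not supported.

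- **That the stated power is wrong.** This needs epsilon below 1, and no document gives a variance or correlation. The grouping of conditions is also open to argument: by receiver the two domes belong together, but by openness the dynamic vent in its open position may sit nearest the open dome. Non-sphericity is plausible, not shown.
- **That any departure from sphericity lowers the power below 80%.** By the planning formula power is still 80.2% at epsilon .96. More importantly, that formula holds the correlation at .5, and step 5 shows true power above 80% in several non-spherical patterns. A flat 72% would be as unsupported as a flat 80%.
- **That the plan commits to an uncorrected F test.** The epsilon sentence follows the power statement and describes an input to it. On correction at analysis the plan is silent.

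It is also fair to say that the inflation of the F test is modest unless the correlations are far apart, and that the 15-20 sample range costs more: the formula gives 67.3% at n = 15 even with epsilon 1. That is a separate matter.

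What the reply leaves standing is the mismatch between the omnibus F and the two pairwise hypotheses, and the unspecified error term. The dispute over grouping does not remove the second. Under either grouping the tested comparisons cross the groups, which is where a pooled error understates the variability. Only if the tested pair were the closely correlated one would it err the other way.

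**Conclusion.** The point holds as a conditional one and as an inexpensive improvement. Section 9 names and powers a test that answers neither stated hypothesis, takes the best-case epsilon without a reason, and leaves sphericity handling open. If sphericity fails in the assumed patterns, type I error at n = 20 is about 5.6% to 7.7% for an uncorrected F and about 7% to 10% for a pooled-error contrast, against about 5% for a paired contrast or a Greenhouse-Geisser test. The stated 80% has little slack by the planning formula, falling just below 80% at epsilon .95, but the loss of true power is possible rather than certain.

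These figures rest on normal data, equal variances, alpha .05, f = .3 and assumed correlations. None of them shows that the trial's own ratings are non-spherical.

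**What to change.** In Section 9:

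1. Name the hypothesis tests: a paired contrast with its own error term for dynamic vent against open dome (streaming) and another for dynamic vent against vented dome (own voice). Neither needs sphericity.
2. State that any within-subject F test will use the Greenhouse-Geisser correction.
3. Keep the disclosed epsilon = 1, but say that the 80% refers to the omnibus F and, by the planning formula, holds only near sphericity. State the alpha and correlation that were used. If they were .05 and .5, show 81% at epsilon 1, 78% at .9 and 72% at .75 for n = 20, and note that true power depends on the covariances and on which means differ.

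Cost: a few sentences and no new data. If sphericity does hold, the corrected omnibus test is slightly conservative (about 4.5%) and its power falls from about 81% to 80%. Each contrast has 19 error degrees of freedom instead of 38, which costs about 2 points of power (for example 79% to 77% when the dynamic vent differs equally from both domes). The stated power will look less favourable.
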